3.2 Study Outcome Measures

3.2.1 Primary Outcome Measure

Decayed, missing, and filled primary tooth surfaces (dmfs) of the children in the study at baseline, and annually for 3 years.

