4 STUDY DESIGN

This is a multicenter, Phase IV, cluster randomized trial to determine whether an intensive intervention of COHS's administering FV (offered 4x a year) and OHP for 2 years in an AI population of children ages 3-6 years in HSCs on the Navajo Reservation vs. usual oral health care made available by the IHS dental providers will reduce the dmfs measure in the children. A cluster randomized design was chosen to reduce the potential for contamination between the 2 intervention groups.

There are approximately 96 HSC classrooms in the NN (based on 2011-2012 school year). We will stratify HSCs on the basis of population size, and randomly assign the HSC classrooms to the 2 arms of the study within the strata. This will make the number of children in each of the 2 arms of the study approximately equal.

The intensive intervention group will have the specially-trained COHS administer FV to the children 4x a year and provide OHP to the parents/caregivers and to the children in the HS classrooms, for 2 years. The other randomized group will have usual oral health care made available by the IHS Dental providers or other community providers.

Enrollment of HSCs will be done over a period of 6 months (in each year, year 1 and year 2). Upon parental consent of the child and parent/primary caregiver consent for her/himself, the HS children from each HSC classroom will be enrolled in the study. Each consented child will participate in the study for up to 3 years. A baseline assessment of the dmfs measure for each child will be done (objective 3.1.1.3 and 3.1.2.1/ outcome 3.2.1 and 3.2.2.1), and a baseline assessment of the dental knowledge, attitudes, and behaviors of the parents/caregivers (objectives 3.1.2.2 and 3.1.2.3/ outcome 3.2.2.2 and 3.2.2.3). The interventions will be administered for 2 years in the Head Start classrooms. The number of interventions a participating child receives will vary with the length of time that the child attends the Head Start class. Annual assessments of the dmfs measure for the children and the dental knowledge, attitudes, and behaviors of the parents/caregivers will be made for 3 years. The 3rd annual assessment is included to determine changes in the outcome measures for up to 18 months after the FV and OHP have ended, to assess the longer term effects of the intervention.

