5 STUDY ENROLLMENT AND WITHDRAWAL

5.1 Subject Inclusion Criteria

Once the HSCs on the Navajo reservation are selected for the study, the HSC will be randomized to the two intervention groups. Subject inclusion criteria include:

- A) Children ages 3-6 years at the time of enrollment in the Navajo reservation HSCs and having a primary caregiver (preferably parent, or the child's legal guardian as documented by the HSC, but another caregiver such as an aunt or grandmother will not be excluded if he or she is the primary caregiver for the child). A parent or legal guardian must be available to give consent for the child to participate in the study. (Note: multiple children from the same family will not be excluded, provided each child is enrolled in the Navajo Head Start Program.)
- B) American Indian, as defined by the tribe, or children of other races/ethnic groups who are in the HS classes on the Navajo reservation (the numbers in this latter group are expected to be very small); and
- C) Parent/caregiver able to read, understand, and sign a consent form for his or her own participation, and willing and able to follow study procedures and instructions.

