7.3 Follow-up Visits for FV

The applications of FV for HS children and OHP will be delivered in the HSCs by the COHS (Group 1). FV will be offered 4x a year for 2 years to children in the classroom on the scheduled day; multiple attempts will be made to provide FV to children not in the classroom on the scheduled day. Group 2 participants will receive usual oral health care made available by the IHS Dental providers (or other dental providers outside the reservation).

Annual dmfs measure of the children, and parent ACASI survey to collect dental knowledge, attitudes, and behaviors will take place annually for 3 years. We will follow the families whose children age out of Head Start and make arrangements for them to complete the child oral health screening and parent ACASI survey at a convenient time and location. All annual follow-up assessments will be done as near as possible to the anniversary of the previous year's oral health screening at that HSC, with the goal of completing them within a month either side of that date.

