10.2 Sample Size Considerations

Sample size is based upon the following assumptions:

1. The primary outcome measure is dmfs, measured at baseline and annually for three years after the beginning of the intervention when the HS children ages 3-5 at enrollment (or possibly 6, depending on the timing of enrollment) will be ages 6-8 (or possibly 9).
2. The test statistic used is the t-test for 2 independent samples, with an inflation factor for the cluster randomized design.^{29, 30}
3. The null hypothesis is no difference in the mean dmfs between the 2 randomized groups 2 years and 3 years after the beginning of the intervention when the children are 5-7 6-8 (or possibly 9) years old. The alternative hypothesis is that there is a difference.
4. Type I error rate will be set at 0.05
5. Type II error rate will be set at 0.20 (Power = 0.80)
6. From the 1999 IHS oral health survey ⁵, the average dmfs for AI children ages 5-7 was 18.55. It was also observed that Navajo children tended to have dmfs measures about 30% higher than the national average for all AI children. Therefore, it was assumed that the average dmfs for Navajo children ages 5-7 will be about 24 under conditions of usual care, with a standard deviation of about 24. We also assumed a 40% reduction in this average dmfs measure for group 1.
7. Based on the experience of other studies the Centers for American Indian and Alaska Native Health have conducted with AI communities, a 70% retention rate was assumed.

8. If subjects drop out of the study due to adverse effects or other reasons, we will ask them to continue in the follow-up even if treatment is discontinued, so that we can perform an “intention to treat” analysis. The “intention to treat” analysis will be the primary analysis of the study.
9. We also assumed an average HS class size of about 20 children and an intraclass correlation of about 0.045, considered to be an appropriate intraclass correlation.³¹

On the basis of the assumptions above, we calculate a need to randomize 52 HSC classrooms, or about 26 HSC classrooms in group 1 and 26 HSC classrooms in group 2. This means that we will need to enroll about 1040 children, or 520 children in group 1 and 520 children in group 2. Sample size calculations are shown in the table in *Appendix B*.

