10.4 Final Analysis Plan

The primary outcome measure will be the difference between groups 1 and 2 on the changes in mean dmfs between baseline and 2-year and 3-year follow-up. Descriptive statistics will be examined first to yield important information about the most appropriate analysis strategies. If the change scores for dmfs are not normally distributed, a log transformation can be made, or a non-parametric test can be used. Longitudinal methods of analysis will be used to examine these repeated, correlated observations within subjects over time.^{32, 33} Other models such as negative binomial regression, mixture models such as ZIP and ZINB will be considered.

Exploratory analyses will first be done to evaluate the trends in the data to determine the most appropriate mean and covariance structures for the data. Graphical displays will be used to assess the mean structure for modeling fixed effects, including scatter plots of the response variable versus time, plots of individual subject profiles, plots of mean profiles, and smooth curve fits to the data. Simple plots of individual subject profiles (dmfs over time) can be very revealing and show whether there is heteroscedasticity in the data (fanning of the curves with time).

Linear mixed models will be used because they can incorporate both fixed and random (subject-specific) effects and permit different covariance structures. A typical example (“random regression”) allows each subject an individual time trend, and treatment effects may cause differences in slope over time. The within-subjects autocorrelation is assumed to be due to these individual trends, on top of which is superimposed independent measurement errors. When analyzing randomized trials, it is assumed that the responses are the values that occur after randomization, because they are influenced by treatment. Thus, it is customary in such trials to consider the baseline value as a covariate, rather than as a response variable. The randomization of subjects in groups or clusters (i.e., HSCs) can also be accounted for in the mixed model with a random effect for group.

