In a series of secondary analyses, hierarchical models will be constructed wherein potential mediators and moderators such as parental knowledge, attitudes and behaviors, are added to the primary outcome model to assess the degree to which these factors explain the relationship between intervention conditions and dmfs changes. For instance, a sequence might be as follows: 1) intervention condition; 2) intervention condition + sociodemographics; and 3) intervention condition + sociodemographics + mediators. Using the approach recommended by Hosmer and Lemeshow,⁴⁰ we will first assess the bivariable relationships of each variable with dmfs. Only those variables with a bivariable relationship at $p \leq 0.25$ will be included in these final models.

The potential of specific variables to have moderating effects will be assessed through the use of interaction terms; for instance, we might find that those with high levels of chronic stress in their lives are less likely to incorporate the important health behaviors that the COHS encourage into their everyday lives.

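### Age at baseline is not pre-specified as a covariate in the primary dmfs model; naming it, with its interaction with visit, is a nearly free but probably small improvement

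*Combined protocol and SAP*

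**What the plan says.** Eligibility (5.1) covers "Children ages 3-6 years at the time of enrollment in the Navajo reservation HSCs". The primary outcome (3.2.1) is "Decayed, missing, and filled primary tooth surfaces (dmfs) of the children in the study at baseline, and annually for 3 years". Section 10.2 puts the children at 6 to 8, possibly 9, at the third annual assessment. Randomisation (5.3.1) is stratified by number of classes and by agency, not by age.

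For the primary analysis, 10.4 describes a linear mixed model with subject-specific time trends and a random effect for the randomised group. On covariates it says only that "it is customary in such trials to consider the baseline value as a covariate, rather than as a response variable". The covariance structure is to be chosen first and the mean structure afterwards, both guided by exploratory work. Complete-case analysis is primary; multiple imputation or modelling of non-response is secondary.

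Age is named nowhere in 10.4. The nearest text is an example of how secondary mediator and moderator models might be built up, which begins "1) intervention condition; 2) intervention condition + sociodemographics" and then adds mediators. Variables enter those models only if their bivariable relationship with dmfs reaches p ≤ 0.25.

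**The concern.** A three-year spread in age at entry matters for an outcome restricted to primary teeth. The youngest children still have most of their primary-dentition years ahead of them, while the oldest are followed to an age at which primary teeth are being replaced. The same baseline dmfs at 3 and at 6 reflects different periods of accumulation and a different remaining set of surfaces at risk. Baseline dmfs therefore takes up part of the age effect but not all of it, and the age effect may differ between the year 2 and year 3 assessments.

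Two things are at stake: precision, and protection against a chance difference in age between the randomised centres. There is also a pre-specification issue. If age is added only after the outcome data have been explored, the choice can be questioned; if it is named beforehand, it cannot.

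**Working it through.** **Inputs from the plan (10.2):** usual-care mean 24, SD 24, a 40% reduction (0.40 × 24 = 9.6 surfaces), alpha 0.05 (taken as two-sided), power 0.80, 20 children per class, ICC 0.045, 70% retention, 520 children and 26 classrooms per arm. Section 2.1 gives a mean dmfs of 19.0 for Navajo children aged 2–5.

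**Assumed, because the documents do not give them:** the age distribution, the clustering of age, and the share R² of the variance in dmfs change that age and age-by-visit explain beyond baseline dmfs.

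**1. The plan's own figure.** The plan gives no figure for age; its only related figure is the sample size. 2 × (24 × 2.802 / 9.6)² = 98.1 per arm. Multiplying by 1 + 19 × 0.045 = 1.855 and dividing by 0.70 gives about 260 (263 if 98.1 is first rounded up to 99). With 14 retained per class (design effect 1 + 13 × 0.045 = 1.585) it gives about 222–225. The stated 520 is not reproduced. The Appendix B table is not in the text available, so an unstated allowance is possible. That is a separate matter. The stated enrolment is used below: 520 × 0.70 = 364 completers per arm, 14 per class.

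**2. Standard error without age.** 24 × √(2/364 × 1.585) = 2.24 surfaces. The SD of 24 refers to dmfs level; no SD of change is given.

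**3. Effect of adding age on the standard error.** Two cases bracket the clustering of age:
- (a) age reduces between-class and within-class variance in proportion: SE ratio = √(1 − R²);
- (b) age varies only within classes. Since 1.585 = 0.955 + 14 × 0.045, SE ratio = √((1.585 − R²)/1.585).

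**4. A rough R² from the documents.** With band midpoints of 3.5 and 6 years, the gradient is (24 − 19.0)/(6 − 3.5) = 2.0 surfaces per year. For age uniform on 3–6 (assumed), the SD is 3/√12 = 0.866, so R² = (2.0 × 0.866/24)² = 0.0052. This mixes sources and concerns level, before baseline dmfs is taken into account. It says nothing direct about change.

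| R² | SE reduction (a) | SE reduction (b) |
|---|---|---|
| 0.52% (documents' gradient) | 0.26% | 0.16% |
| 5% (assumed) | 2.5% | 1.6% |
| 10% (assumed) | 5.1% | 3.2% |

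Against an SD of 24, R² = 5% corresponds to √0.05 × 24/0.866 = 6.2 surfaces per year, about three times the documents' gradient.

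**5. Power, 364 per arm, 14 per class, case (a).** For 9.6 surfaces, power is 99.0% without age, 99.0% at R² = 0.5% and 99.3% at 5%. For a 25% reduction (6.0 surfaces) it is 76.4%, 76.6% and 78.5%.

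**6. Chance imbalance in mean age.** The 95% limit is 1.96 × SD(age) × √(2/364 × (1 + 13 × ICC of age)). An SD of 0.5 with age ICC 0 gives 0.07 years; an SD of 0.866 with age ICC 0.10 gives 0.19 years. At 2 surfaces per year that is about 0.15–0.4 surfaces. This is already contained in the SE of 2.24 and is not a further loss.

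**The case against.** The case against is that the plan leaves the mean structure open, so age may still be added; that baseline dmfs absorbs part of the age effect; that randomisation protects the comparison; and that power at the stated effect is already about 99%. All of this stands as a limit on size. None of it supplies pre-specification, and an open mean structure is the reason to name the covariate now.

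A reader might also infer several stronger things that the documents do not support:

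- **That age has been relegated to a secondary model.** The sequence in 10.4 is offered as an example and does not name age. Age is unspecified, not excluded.
- **That older entrants receive fewer varnish applications.** Section 4 says "The number of interventions a participating child receives will vary with the length of time that the child attends the Head Start class". It ties the number to attendance, not to age. The inference is reasonable, but exposure to the programme arises only in Group 1. It is thus an age-by-treatment question, which age and age-by-visit terms do not answer.
- **That ageing out is the main route of loss.** No reasons are ranked, and section 7.3 says "We will follow the families whose children age out of Head Start". Leaving Head Start is not leaving the study.
- **That a complete-case analysis without age is biased.** If retention depends on age equally in both arms and the effect does not vary by age, completers have the same age mix in each arm and the difference is unbiased. Bias needs arm-differential retention by age or an effect that varies by age; the documents show neither. As an invented illustration, take equal numbers of younger and older children, 85% retention of younger children in both arms, and 60% against 50% of older ones. The older share among completers is then 0.60/1.45 = 0.414 against 0.50/1.35 = 0.370. A 5–10 surface difference in change by age group gives a bias of 0.2–0.4 surfaces, small beside an SE of 2.24. If the effect did vary by age, the proposed terms would not recover the effect in all enrolled children.
- **That age could explain a fifth of the variance.** Against an SD of 24 this needs √0.20 × 24/0.866 = 12.4 surfaces per year, about six times the documents' gradient.

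**Conclusion.** The point holds as a low-severity, nearly free improvement. Section 10.4 does not name age in the primary model, although the entry range and the primary-tooth outcome make it a plausible predictor of dmfs change. The benefit is some precision, protection against chance age imbalance between centres, and a covariate choice fixed before outcomes are seen.

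The size is not known from the documents and may be small: roughly 0.2% off the standard error on the documents' rough gradient, and 1.6–2.5% if age explains 5% of the variance in change. These figures rest on a uniform age distribution over 3–6 years, 364 completers per arm, 14 per class, ICC 0.045 and, for the gradient, an SD of 24. The gain for change scores could be larger than the cross-sectional gradient suggests, but that cannot be shown from the plan. Leaving age out does not in itself bias the randomised comparison.

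**What to change.** In 10.4, state that age at baseline screening (continuous) and its interaction with visit are fixed covariates in the primary model, alongside baseline dmfs and the random effect for the randomised group. State that they are not subject to the p ≤ 0.25 screen, and include the same terms in the imputation model. The wording should apply whichever distributional form is finally chosen among the regression models.

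The cost is a sentence or two and a few child-level degrees of freedom. No new data are needed: age must be known to apply 5.1, and the enrolment survey in 7.2 collects the children's demographic information.

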11 SOURCE DOCUMENTS AND ACCESS TO SOURCE DATA/DOCUMENTS

Study records will be maintained for each child and parent/caregiver enrolled in the study. Source documents include all paper and electronic data files collected at the child/family level such as: informed consent forms, oral health screening results, delivery of fluoride varnish; attendance records of the children and parents/caregivers at OHP encounters; parent/caregiver questionnaires assessing dental knowledge, attitudes, and behaviors; use of dental and medical services for oral health problems; intervention costs; and records of the activities of the COHS.

There will also be source documents collected at the HSC level. These will include characteristics of the HSC, FV inventory records, and OHP activities at the HSC-level.

Source documents will be maintained in locked file boxes during data collection periods and subsequently transferred to a locked file cabinet at the RC2 NN field office. After annual enrollment is complete, participant consent forms will be transported to UCD for long term storage in accordance with HIPAA regulations.

12 QUALITY CONTROL AND QUALITY ASSURANCE

Ultimate responsibility for implementation and maintaining quality assurance and quality control systems with written standard operating procedures to ensure that the trial is conducted and data are generated, documented and reported in compliance with the protocol resides with the principal investigator of the intervention trial. The project coordinator and field coordinator will provide regular reports on the fidelity and administration of the intervention to the PI.

The Center for Native Oral Health Research (CNOHR) also has responsibility for monitoring progress via monthly meetings to review and evaluate the performance of the intervention trial. Their role is to ensure that the intervention trial conducted and data generated are in compliance with the protocols, good clinical practices and the applicable regulatory requirements. The CNOHR's internal governance groups (Executive Committee, CNOHR Coordinating Committee) meet monthly to ensure the intervention trial is meeting objectives and to consider all aspects of the project for oversight, feedback and suggestions enhancing future progress along with monitoring of expenditures and cost allocations as the project progresses. Their oversight includes verification that the PI has secured appropriate agreements from all involved parties, has adequately secured the data/documents and reports and all protocols and standard operating procedures have been followed and quality assurance and quality control of the data, its reliability and assessment have been appropriately recorded, maintained and evaluated during the intervention trial. CNOHR members of the statistics and data coordinating center will work closely with the leadership and staff of the intervention trial to provide statistical, data management, programming, methodological and electronic communications support. They will also have oversight responsibility to ensure compliance of the intervention trial with the protocols, the accuracy and completeness of the documents, reports, notes, etc. and quality management of overall intervention program.

CNOHR Community Advisory Committee, a 6-member committee representing tribal governments and health organizations and other community organizations participating in the CNOHR research activities, will meet at least once annually to review progress of the intervention trial and its impact/benefit on the communities being served.

13 ETHICS/PROTECTION OF HUMAN SUBJECTS

13.1 Ethical Standard

The PI will ensure that this study is conducted in full conformity with the principles set forth in The Belmont Report: Ethical Principles and Guidelines for the Protection of Human Subjects of Research of the U.S. National Commission for the Protection of Human Subjects of Biomedical and Behavioral Research (April 18, 1979) and codified in 45 CFR Part 46 and/or the ICH E6; 62 Federal Regulations 25691 (1997).

13.2 Institutional Review Board

This protocol, the associated informed consent documents, recruitment and retention materials, forms, and COHS curriculum and intervention materials for this study will be reviewed and approved as required by the University of Colorado Multiple Institutional Review Board (COMIRB) and the Navajo Nation Human Research Review Board (NNHRRB) prior to the start of the study. Any amendments to the protocol or consent or recruitment materials will also be approved by these committees before implementation.

